#### **5.4 Action Mechanism**

Same as the operating principle.

#### **5.5 Scope of Study**

It is proposed to conduct this study in 11 medical institutions with qualifications for clinical studies.

### **6. Intended Use, Contraindications and Precautions of Product**

#### **6.1 Intended Use**

THERANOVA dialyzers are indicated for treatment of chronic and acute kidney failure by HD.

#### **6.2 Contraindications**

There are no known contraindications for the use of the Theranova 400.

#### **6.3 Precautions**

The dialyzers are for single use only.

Follow the product instructions to use the product.

The quality of the product is guaranteed for first use only, and only when prepared and used according to the procedures described. Reprocessing this dialyzer may cause serious damage to the product resulting in patient hazard.

Treatment parameters should be chosen within the limitations given in the specification table.

The dialyzer is used together with a dialysis device that can precisely control and monitor the ultrafiltration rate and blood in the dialysate circuit (leakage detector).

Expanded removal of molecules may lead to increased removal of certain drugs. Clinicians should consider this when prescribing the device and make any necessary dosing adjustments.

Do not apply isolated/sequential ultrafiltration when using THERANOVA dialyzers, due to higher permeability for larger plasma proteins such as free haemoglobin. In dialysis patients, plasma free haemoglobin is usually present in low concentrations (up to 239 mg/L ). During isolated/sequential ultrafiltration, free haemoglobin is filtered and concentrated in the dialysate compartment. This leads to a reddish coloration of the ultrafiltrate which may trigger the internal blood leak detector.

[figure not shown]
### **7. Overall Design**

## 7.1 Study Design

A randomized, controlled, open-label, parallel, multicenter study.

The study population consists of patients with kidney failure on a stable HD and/or HDF prescription. A sufficient number of patients will be enrolled to ensure 272 patients are randomized 1:1 to either Theranova 400 (136 patients) or FX 800 (136 patients). All patients will receive one (1) session of mid-week therapy with either Theranova 400 or FX 800. A follow-up session is scheduled at the next treatment (end-week) session, but prior to treatment commencement (See Figure 1).

**Figure 1: Clinical Trial Design Flow**

### 7.1.1 Study Purpose

To demonstrate non-inferiority of Theranova 400 compared to FX 800 HDF, in regard to the RR of  $\lambda$  FLC, and  $\beta$ 2-MG.

### 7.1.2 Rationale of Study Design

- (1) Selection of clinical study methods: randomized, parallel-controlled, open-label, multicenter study.
- (2) Randomization: In this trial, central randomization system is used for randomization, and stratified block randomization method is selected. Using the center as a stratification factor, all screened patients are randomly assigned to the test group or the control group at a ratio of 1:1.
- (3) Open-label: Investigators and patients are not blinded due to differences in the appearance and operation between investigational products and control products. In

addition, the RRs of  $\beta2$ -MG and  $\lambda$  FLC in this trial are not affected by subjectivity of investigators or patients, so an open-label design is utilized in this trial.

(4) Parallel control: There is no similar product available yet. The hollow fiber HD/filter (model: FX 800 HDF) is similar to the investigational product in intended uses, structures and performances as the control product in this trial.

### 7.1.3 Measures to Reduce and Avoid Bias

- (1) Multicenter clinical study: Patients are from multiple study sites, avoiding the bias of test results caused by systematic errors in a single study site.
- (2) A randomized design is utilized in this study to ensure comparability between groups and reduce selection bias.
- (3) Participating investigators and operators in various sub-sites will be trained on the use of the Theranova 400 Dialyzer; the study must be conducted in strict accordance with the clinical study protocol and China's standard operating procedures for HD.

### 7.1.4 Study Medical Device and Control Device

(1) Study Medical Device

Product name	Hollow fiber dialyzers with medium cut-off membrane
Model and Specification	Theranova 400
Registrant	Gambro Dialysatoren GmbH
Shelf Life	Refer to IFU
Storage	<30°C/86°F
Structural composition	The membrane material used in Theranova 400 is a composite of polyaryl ether sulfone (PAES) and polyvinylpyrrolidone (PVP). Both ends of the dialyzer are filled with polyurethane (PUR) hollow fibers to separate the blood chamber from the dialysate chamber. The inner diameter of each hollow fiber is approximately 180 $\mu$ m, and the wall thickness is approximately 35 $\mu$ m. The effective length of the membrane is 236 mm. The number of hollow fibers of Theranova 400 is about 13,000, and the surface area of Theranova 400 is 1.7 m  . The material used for the dialyzer housing and end caps is polycarbonate.
Scope/Intended Use	THERANOVA dialyzers are indicated for treatment of chronic and acute kidney failure by HD.

(2) Control Device:

Product name	Hollow fiber hemodialysis filter
Model and Specification	FX 800 HDF
Registrant	Fresenius Medical Care AG & Co., KGaA.
Registration No.	GXZJ 20193101929
Shelf Life	Refer to IFU
Storage	Refer to IFU
Structural composition	This product consists of fiber membrane, housing, packaging material, top cover, sealing ring, blood protective cap and dialysate protective cap. The materials of hollow fiber membrane, housing, packaging, topcover, sealing ring, blood protective cap and dialysate protective cap are a mixture of polysulfone fiber-polyvinylpyrrolidone, polypropylene, polyurethane, polypropylene, silicon resin and polypropylene, respectively. This product is sterilized by flowing steam, and it is disposable.
Scope/Intended Use	The product is indicated for conventional HD or HDF treatment.

## 7.1.5 Patient Selection

### 7.1.5.1 Inclusion Criteria

All of the following criteria must be met for the patient to be eligible for participation.

1. Patients aged  $\geq 18$  years old and  $\leq 80$  years old, regardless of gender;
2. Patients who are able to sign informed consent form (ICF) after an explanation of the proposed study;
3. Patients who receive in-center HD treatment at a site that routinely implements high flux dialysis and HDF;
4. Patients who have been stable receiving in-center HD/HDF for  $>3$  months prior to study enrollment;
5. Patients with kidney failure receiving maintained HD treatment with a history of thrice weekly HD, and at least 1 HDF session within 1 month prior to the study shall be judged by the investigator;
6. Patients who have an adequate arteriovenous (AV) fistula or graft, or dual-lumen tunneled catheter capable of providing a blood flow rate (QB) of at least 250 mL/min;
7. Patients have no changes in dialysis prescription (dialyzer, time, dialysis fluid flow rate (QD), QB, sufficient dialysis anticoagulation, and stable prescribed doses) over last 6 treatments as judged by the investigator. The dialysis treatment time should be 3.5 to 4.5 hours per session with minimum QB of 250 mL/min and QD of 500 mL/min;

---

8. Patients with a minimum total convective volume (including ultrafiltration (UF)) of 16 L post-dilution for the most recent HDF treatment;
9. Patients who have  $Kt/V_{urea} > 1.2$  for the last 2 measurements, with the most recent  $Kt/V_{urea}$  measurement taken within 4 weeks before or during study screening.

### **7.1.5.2 Exclusion Criteria**

Patients who meet any of the following criteria will be excluded from the study:

1. Patients who have acute kidney injury with the chance for recovery;
2. Pregnant and lactating women;
3. Patients diagnosed with a New York Heart Association (NYHA) Class IV congestive heart failure, or acute coronary syndrome, and/or who have suffered a myocardial infarction within 3 months prior to the start of the study;
4. Patients with known hemodynamic instability, anemia (hemoglobin <90 g/L), and/or patients with hemoglobin >130g/L for coagulation risk;
5. Patients with active or ongoing infection as per investigator's judgement (e.g C-reactive protein [CRP] level more than 5 folds of normal);
6. Patients who are severely malnourished or with significant disease that interferes with liver synthetic function ( e.g. with serum albumin <30 g/L);
7. Patients with positive serology tests for Hepatitis B surface antigen, Hepatitis C total antibody, and advanced liver, or pulmonary disease as judged by the investigator;
8. Patients with positive serology tests for human immunodeficiency virus (HIV), Syphilis;
9. Patients receiving immunosuppressive treatment or with autoimmune disease;
10. Patients with a history of solid tumors requiring anti-cancer therapy in the past or next 6 months, or with a life expectancy of <1 year, or patients with history of hematology neoplasm;
11. Patients who are pre-scheduled for a living donor kidney transplant within the next 1 year, who plan a change to peritoneal dialysis (PD) within the next 1 year, or who require single-needle dialysis therapy;
12. Patients who have had an allergic response to polyarylethersulfone (PAES) or polysulfone (PS) membrane or have history of poor tolerance to dialyzers with synthetic membranes;
13. Patients with a history of severe mental disorders who are unable to provide consent or comply with study procedures as assessed by the investigator;
14. Patients who are currently participating in or have previously participated in other interventional clinical studies during the past 30 days;
15. Patients with any comorbidity possibly conflicting with the study as judged by the investigator.

### **7.1.5.3 Study Suspension and Discontinuation**

#### **7.1.5.3.1 Criteria for Study Suspension and Discontinuation**

The main purpose of study suspension or discontinuation is to protect rights and interests of patients, ensure the study quality and avoid unnecessary economic losses. Study suspension or discontinuation will be performed in case of the following circumstances (including without limitation):

- (1) Clinical study institutions and investigators assess that the risks outweigh the benefits if the study continued;
- (2) The Ethics Committee finds that the rights and interests of patients cannot be guaranteed;
- (3) Discontinuation of study is required by the Sponsor for various reasons;
- (4) Discontinuation of study is instructed by regulatory authorities.

#### **7.1.5.3.2 Procedure for Study Suspension and Discontinuation**

When deciding to suspend or discontinue the study, the Sponsor shall promptly inform the study management departments of the clinical study institutions who will inform the investigators and the Ethics Committee, and provide them with relevant data supporting this decision. The resumption of the clinical study needs approval of the Ethics Committee. After the end of the clinical study, the sponsor shall inform the Shanghai Medical Products Administration in writing.

### **7.1.5.4 Patient Withdrawal**

#### **7.1.5.4.1 Criteria for Patient Withdrawal:**

All patients are entitled to withdraw at any time throughout the study. Patients will withdraw from the study under the following circumstances:

- (1) Withdrawal of ICF;
- (2) AEs/serious adverse events (SAEs) occur that make treatment inapplicable;
- (3) Serious protocol violation;
- (4) Death;
- (5) Pregnancy;
- (6) Kidney transplantation;
- (7) Switch to PD;
- (8) Other reason.

---

**Process of Withdrawal from the Study:**

- (1) Details of the time and reasons for withdrawal from the study are recorded in the electronic case report form (eCRF);
- (2) Patients' data will not be collected after their withdrawal from the study, but patients who withdraw from the study due to AEs must be followed up until the AEs are stable or resolved or are deemed no need of further follow-up by investigators.

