### **8.4 Expected Dropout Rate**

It is estimated that the expected ratio of cases with dropout or serious protocol violations is about 5%.

This ratio refers to the proportion of patients who ultimately cannot be evaluated for primary efficacy on the per-protocol analysis set. This part of patients are those who have been dropped out or have serious protocol violation (affecting the evaluation of primary endpoints) after confirmed by the principal investigator (PI).

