## **8.9 Criteria for Selection of Patients Included in the Analysis and Justification**

- (1) Intention-to-treat FAS: Includes all randomized patients. Patient assignment will be based on the treatment randomized.
- (2) Per-Protocol Set (PPS): Is a subset of the FAS and meets the following requirements: Patients were randomized to the respective treatment at themid-week treatment day dialysis session and did not have any major protocol deviations that could affect the assessment of the primary endpoint when dividing the patient population. Major protocol deviations when dividing the patient population are defined as follows: :
  - 1) The actual QB of the patient is  $< 220$  mL/minute for a duration of more than 30 min or for a total duration of  $> 60$  minute at themid-week treatment day dialysis session; patients in control group who actually do not achieve at least 16 L convective volume (including UF)
  - 2) The actual dialysis time of the patient is  $< 210$  minute at themid-week treatment day dialysis session.
- (3) Safety analysis set (SS): Includes all enrolled patients (ICF signed) that have been treated. Patient assignment will be based on actual treatment received.

The analysis of the primary endpoint will be based on the PPS, with a supportive analysis of the primary endpoint based on the FAS. Unless otherwise specified, the remaining analyses will be based on the FAS. All safety related analyses will be based on the SS.

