For all AEs associated with patients, a full description of the event should be recorded in the eCRF including the date and time of onset (when the signs and symptoms of the event began), outcome, seriousness, severity, event description, actions taken, and causal relationship of the AE or SAE. Investigators should review and reference the severity (refer to Table 2) and causality definitions (refer to Table 3) when determining relationship of the AE or SAE to the study device and procedure. The investigator may also discuss the event(s) with the Sponsor's Medical Monitor or designee.

For all AEs associated with users or other persons (not the study patient), a full description of the event should be recorded on the paper AE form and sent via email to Sponsor designee and Baxter Global Patient Safety Medical Device Vigilance

[REDACTED].

All AEs and SAEs should be actively solicited and documented in the eCRFs, no matter how common they are for a patient and regardless of the causality assigned by the investigator. Additionally, any AE and SAEs voluntarily reported by the patient should be recorded in the eCRF and verified by the investigator or designee with the relevant source documents.

The outcome/resolution of all AEs and SAEs will be determined by the investigator and documented in the eCRF. Investigators will follow all unrelated AEs and SAEs until resolution, stable, or the end of the study, whichever occurs first, and follow all study device-related and procedure-related AEs and SAEs until resolution or stable, including following the patient after the end of the study if necessary. Outcomes and other relevant information obtained after the end of the study will be reported via the paper AE form and sent via email to Baxter Global Patient Safety Medical Device Vigilance [REDACTED].

For the outcome categories that can be used in the eCRF by the investigator refer to Table 4.

During the study period, if a patient experiences an AE which is considered causally related to a Baxter medicinal/drug product (not the study medical device or comparator), the event shall be forwarded by the investigator or designee within 24 hours of becoming aware of the AE to Baxter

Global Patient Safety [REDACTED] for assessment as per Baxter's process for case processing of spontaneous reports.

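### Data collection stops at any withdrawal not caused by an AE, so a treated patient withdrawn for a protocol violation misses the end-week AE review, contrary to the protocol's own AE rules

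*Protocol*

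**What the plan says.** Protocol Section 7.1.5.4.1 introduces its list of reasons with "Patients will withdraw from the study under the following circumstances". The third reason is "Serious protocol violation", without a definition. The process of withdrawal that follows states that patients' "data will not be collected after their withdrawal from the study". Its only exception is that "patients who withdraw from the study due to AEs must be followed up until the AEs are stable or resolved", or until the investigator sees no need for more.

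Other sections bear on the same patients:

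- **Section 7.2.1.4** places the one scheduled post-session AE review at the next (end-week) session. It covers the treatment day and the day after.
- **Section 13.1.2** has AEs documented from consent to the final assessment visit. It also tells investigators to "follow all study device-related and procedure-related AEs and SAEs until resolution or stable, including following the patient after the end of the study if necessary".
- **Section 8.9** defines the FAS: "Includes all randomized patients". The Safety Set holds all treated patients. The primary analysis uses the PPS, and the FAS analysis is supportive.
- **Section 8.4** uses the term serious protocol violation for patients who cannot be evaluated on the PPS, once the principal investigator has confirmed it. It names them alongside dropouts in a single allowance of about 5%.

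**The concern.** Each patient has one study session, and the AE review comes afterwards. If a violation is recognised during or just after the session and the patient is withdrawn, the review falls after withdrawal and is not collected. The patient has been exposed and stays in the Safety Set, whose size is the default denominator for percentages (SAP Section 7.6). AEs in the unobserved interval cannot enter the numerator.

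A site also receives conflicting instructions. If a treated patient is withdrawn for a violation while a device-related AE that did not cause the withdrawal is ongoing, the withdrawal process says to stop collecting and Section 13.1.2 says to continue.

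Efficacy is exposed more narrowly. If withdrawal takes effect before the post-dialysis sample, an obtainable reduction ratio becomes missing. The supportive FAS analysis must then impute it (SAP Section 17.1.3). The FAS-based secondary endpoints are not imputed (SAP Sections 8.1 and 17.2.2), so the patient drops out of those.

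**Working it through.** **1. The rule applied to a treated patient**

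| Reason for withdrawal | Withdrawal process (7.1.5.4) | AE rules (7.2.1.4, 13.1.2) | Analysis sets (8.9) |
|---|---|---|---|
| AE | Follow until stable or resolved | Document and follow | FAS and Safety Set |
| Serious violation or other non-AE reason | Collect nothing further | Document to the final visit; follow related AEs | FAS and Safety Set |

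The second row contains the contradiction. Section 13.1.2 makes no exception for the reason for leaving.

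**2. When the primary outcome is lost through this rule**

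The nearest list of qualifying events is the set of major deviations in Section 8.9. Reading the undefined term as that list is an inference.

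- *Blood flow under 220 mL/min, for over 30 minutes or for over 60 minutes in total.* This can be recognised mid-session. If withdrawal takes effect then, the post-dialysis sample and post-dialysis safety assessments are lost.
- *Session under 210 minutes.* For early stops not due to the dialyzer, the sampling table in Section 7.2.3.3 allows a sample only after at least 210 minutes. The outcome is already unprovided for, whatever the withdrawal rule says.
- *Control convective volume under 16 L.* This is a session total, known at about the time of the sample (240 ± 5 minutes). Withdrawal can hardly precede sampling, and nothing says that data already collected are discarded.

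**3. The plan's own figures**

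Inputs from Sections 8.2 and 8.3: one-sided alpha 0.025, power 90%, true difference 0, SD 9.09 and margin 3.783 for λ FLC, SD 14.28 and margin 7.848 for β2-MG. The noncentral-t sample size is 123 per arm for λ FLC and 71 for β2-MG. Multiplying by π/3 for the Wilcoxon test gives:

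- λ FLC: 123 × π/3 = 128.8, so 129 per arm.
- β2-MG: 71 × π/3 = 74.4, so 75 per arm.
- Inflation: 129 / 0.95 = 135.8, so 136 per arm and 272 in total.

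All agree with the plan. The allowance is 272 − 258 = 14 patients (14/272 = 5.1%), about 7 per arm. It is not split between dropouts and violations, so the number treated and then withdrawn for a violation lies between 0 and 14 within the planned allowance.

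**4. Size for safety**

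The documents give no post-session AE risk, so 2%, 5% and 10% per patient are assumed. With k unreviewed patients, the expected number with an unseen AE is k × p. The chance of at least one is 1 − (1 − p)^k.

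| k | p = 2% | p = 5% | p = 10% |
|---|---|---|---|
| 7 | 13% | 30% | 52% |
| 14 | 25% | 51% | 77% |

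At k = 14 the expected number is 14 × p = 0.28, 0.70 or 1.40 patients.

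**5. Size for the FAS analysis**

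Suppose k of 136 patients in one arm lose the outcome and their true reduction ratio is D points below that of the others (D assumed). If imputation treats them like the others, that arm's mean is overstated by k/136 × D.

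- k = 7, D = 5: 7/136 × 5 = 0.26 points, 7% of the 3.783 margin.
- k = 7, D = 10: 0.51 points, 14%.
- k = 7, D = 20: 1.03 points, 27%.
- k = 1, D = 20: 0.15 points, 4%.

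Loss in the Theranova 400 arm would favour non-inferiority, and loss in the control arm would work against it. Power is a minor matter: for λ FLC, by a Wilcoxon-adjusted normal approximation, it is about 90.4% with 129 per arm and 91.8% with 136.

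**The case against.** The best defence is that the protocol never says these patients are withdrawn mid-session. The term is undefined. Section 8.4 names violators separately from dropouts, which suggests that they may stay in the study and leave only the PPS. Section 14.2 has low blood flow and short sessions recorded and graded, without mentioning withdrawal. Section 9.10 assigns patients to analysis sets before database lock, long after the session. Some bad sessions will involve an AE that itself causes withdrawal, and the exception then applies. Section 13.1.2 separately protects follow-up of related AEs.

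This limits the point without removing it. Withdrawal for a serious violation is mandatory as written, a site could apply it at the session, and Section 13.1.2 is one side of the conflict, so it cannot also settle it.

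A reader might infer more than the documents support:

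- **That violators generally lose their FAS outcome.** Step 2 leaves only early withdrawal, with low blood flow the clearest case.
- **That the loss differs by arm because the 16 L criterion applies only to controls.** That trigger is the least able to precede the sample.
- **That 14 patients are affected.** This is a ceiling that includes ordinary dropouts, some perhaps never treated.
- **That the rule contradicts the FAS and Safety Set definitions.** Those fix who is analysed, not what is collected, and the SAP foresees missing FAS outcomes through multiple imputation and a tipping-point analysis. The contradiction is with the AE rules.

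**Conclusion.** The point stands in limited form. As written, a treated patient withdrawn for a reason other than an AE loses the only scheduled post-session AE review while still counting in the Safety Set. The withdrawal process and Section 13.1.2 cannot both be followed when an AE did not cause the withdrawal. These conclusions rest on the text alone.

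The size is uncertain: 0 to 14 of 272 patients within the planned allowance. The AE probabilities and FAS shifts above depend on assumed risks and differences, and the larger ones take the whole allowance to be affected. Loss of a primary outcome also requires withdrawal before the post-dialysis sample. The primary PPS analysis is unaffected, because it excludes major deviations anyway. The effect falls on the AE summaries and their between-arm Fisher tests, the supportive FAS analysis and the FAS-based secondary endpoints. The plan should be corrected, but its main conclusion is not threatened.

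**What to change.** Reword the withdrawal process in Section 7.1.5.4 and reconcile it with the sections that depend on it:

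1. For every patient who started the study session, collect the already scheduled post-dialysis assessments that can still be obtained, and the end-week AE review, unless the patient withdraws consent to data collection.
2. Define serious protocol violation, and say how it relates to the wording in Section 8.4 and the major deviations in Section 8.9.
3. State that a protocol violation leads to exclusion from the PPS and does not by itself end data collection. The withdrawal criterion need not be deleted for this.
4. Align the withdrawal process with Section 13.1.2, so that AE documentation and follow-up do not depend on the reason for withdrawal.

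The sample size stays at 272 and no new procedure is added. The cost is an amendment to the wording, plus slightly more data collection and cleaning for a few patients. Outcomes from sessions under 210 minutes would remain missing where Section 7.2.3.3 makes no provision for the sample.
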